8 UNBLINDING UPON COMPLETION OF PART A

Immediately after Part A (double-blind phase) of the study completes and the database is cleaned and locked, the responsible CRO(s) will follow their SOPs to unblind the Part A. . A blinded data review will be performed (per ICH E9) before the database is locked and before the study groups are unblinded. Primary and secondary efficacy analyses are final and will not be modified. Exploratory analyses that do not involve the primary or secondary efficacy analyses are subject to modification.

9 STATISTICAL METHODS

The software used for all summary statistics and statistical analyses will be SAS® (SAS Institute, Inc.)¹ Version 9.2 or later.

Most continuous data will be summarized with the following descriptive statistics unless otherwise noted: number of observations, mean, SD, median, minimum, and maximum; interquartile ranges will be provided as appropriate. Categorical data will be summarized with frequencies and percentages.

Missing data will not be imputed unless otherwise documented in this SAP.

Unless stated otherwise, statistical tests conducted will be two-sided at an α level of 0.05. No adjustment for multiplicity will be made unless otherwise stated in the following sections.

For presentation of data, the mean and median will be presented to 1 decimal place greater than the original data, SD will be to 2 decimal places greater than the original data, and the minimum and maximum will have the same number of decimal places as the original data. P-values, if any, will be reported to three decimal places; p-values less than 0.001 will be reported as p<0.001. The format for minimum and maximum will be "Min, Max". Standard deviation will be abbreviated as "SD".

If a subject is incorrectly dosed, the tables, figures and listings based on the ITT or mITT analysis sets will include a footnote indicating the dosing error.

9.1 Subject Disposition

Subject disposition data will be summarized for all screened subjects. A table will be presented by treatment group, all tozadenant and overall and will include:

- Number of subjects screened
- Number of subjects in ITT

Statistical Analysis Plan for Final Analysis FINAL v1.0 - 19 May 2015 Biotie Therapies, Inc. – TOZ-CL05 (Part A)

- Number (%) of subjects in SS
- Number (%) of subjects in mITT
- Number (%) of subjects in PPS
- Number (%) of subjects complete 24 weeks of treatment
- Number (%) of subjects who prematurely withdrew along with reasons for withdrawal

A listing of all subjects screened along with data on their disposition, will be provided, including reasons for non-participation for screen failures.

A table will be presented that will summarize number and percent of subjects enrolled at each site by treatment group for the ITT.

9.2 Protocol Deviations and Violations

Protocol deviations and violations (PDVs) will be identified by the Sponsor prior to database lock and flagged for exclusion from the PPS population. The protocol deviations and violations are categorized and designated major or minor, and finalized prior to database lock and unblinding. Categories include but are not limited to the following: inclusion criteria, exclusion criteria, study drug, assessment - safety, assessment - efficacy, visit window, lab/ endpoint data, visit window, informed consent, anti-PD medication (increased or additional/new), non-anti PD medication (increased or additional/new), PD diary violation and other.

If there is a significant number of major protocol deviations and violations, they will be summarized by deviation/violation category and treatment group. Otherwise, all PDVs will be documented in a data listing only.

9.3 Treatments

9.3.1 Extent of Study Drug Exposure

The number of days of exposure to study drug will be summarized by treatment group in the SS. Descriptive statistics (n, mean, standard deviation, median, minimum, and maximum) for the total number of tablets taken, number of tablets returned and number of tablets lost will be displayed. Compliance with study drug will be calculated as the number of doses taken divided by the scheduled number of doses taken, expressed as a percentage. Compliance will be summarized overall and by scheduled weeks (Week 2, 6, 18 and 24) for each treatment group for the safety analysis set. The reason for not returning tablets is captured on the CRF and will be presented in the data listings.

9.3.2 Concomitant and Prior Medications other than Anti-PD Medications

Prior and concomitant medications other than anti-PD medications will be coded to a preferred name according to the WHODRUG coding dictionary version or higher. Prior medications are defined as those medications that had the last dose taken prior to the first dose of study drug given, whereas, concomitant medications are defined as medication ongoing at baseline, or medication initiated on or after the first dose day of study drug administration. The number and percent of subjects will be summarized for prior and concomitant medications for each preferred term (PT) by treatment group in the SS. All prior and concomitant medications taken during the study will be listed for each subject including dosage and indication.

9.3.3 Concomitant and Prior Anti-PD Medications

Prior and concomitant anti-PD medications will be coded to a preferred name according to the WHODRUG coding dictionary version <<version>> or higher. Prior anti-PD medications are defined as those medications that were taken for the disease and stopped or were modified since the time of diagnosis. Concomitant anti-PD medications are defined as those medications that were taken for the disease on or after the day of first dose of study drug. The number and percent of subjects will be summarized for prior and concomitant anti-PD medications for each preferred term (PT) by treatment group in the SS. All prior and concomitant anti-PD medications will be listed separately for each subject.

CONFIDENTIAL

Any changes to anti-PD regimen during or after the study treatment period will be presented in a frequency table by treatment group and as a subject data listing. The summary will be based on the safety analysis set and percentages will be based on the number of subjects in the safety analysis set.

The last dose of anti-PD medication taken the evening before the day when UPDRS part III test are done in defined "ON" state at Screening, Baseline (Pre-dose Day 1), Weeks 2, 6, 12, 18 and 24 will be documented in a subject data listing along with the date and time of UPDRS Part III performed before anti-PD medications. The subject data listing will include medication/treatment, dose, number of tablets or capsules taken, frequency, date of last dose and time of last dose.

9.3.3.1 Total Levodopa Dose at Baseline

The total levodopa dose at baseline will be calculated (Section 5.10.1) and summarized by treatment group.

9.3.3.2 Total Levodopa Equivalents at Baseline

The total levodopa equivalent dose at baseline will be calculated (Section 5.10.2) and summarized by treatment group.

9.4 Demographic and Baseline Characteristics

Demographic and baseline characteristics will be summarized descriptively for the ITT, SS, mITT and PPS by treatment group and total tozadenant. These variables include:

- Gender
- Race and ethnicity
- Age (years)
- Body weight (kg)
- Height (cm)
- Body Mass Index (BMI) (kg/m²)
- Caffeine Intake (mg/day)
- Duration of PD (years)
- Hoehn and Yahr Staging of PD in ON state and OFF state (best estimate)

An analysis of variance (ANOVA) will be performed independently for age, body weight, height, body mass index, duration of PD, duration of levodopa treatment, with treatment group as a class variable. Age will also be classified into 3 categories (\geq 30 to 54, \geq 55 to 68 and \geq 69 to 80 years). Within each ANOVA, each tozadenant treatment group will be compared to placebo

through "Estimate" statements. Chi-square tests will be performed for age (categorized), gender, race, ethnicity, caffeine intake and Hoehn and Yahr Staging of PD in ON state and OFF state (best estimate) comparing each tozadenant treatment group to placebo. Additionally, an ANOVA or Chi-square test with region/country as a factor will be performed on the each variable listed above, to determine if there are any country differences.

CONFIDENTIAL

9.5 Medical History events

Medical conditions resolved at randomization and medical conditions ongoing at randomization will be summarized by MedDRA system organ class (SOC) and PT for the SS by treatment group. All medical conditions collected on the eCRF will be included in the listings.

9.6 Efficacy Analyses

All analyses of the primary and four key secondary endpoints will focus on the comparison of tozadenant 120 mg BID vs. placebo followed by a comparison of tozadenant 60 mg BID vs. placebo. Adjustment for multiplicity for p-values from the analyses of the four key secondary endpoints will be performed per **Section 9.6.6**. All other p-values derived from analyses of the remaining efficacy endpoints will be reported as nominal without adjustment for multiplicity.

To explore treatment differences by geographical location, a country/region term will be included in the analysis model. If there are insufficient number of patients represented in a country, patients by be pooled using a specific criterion that will be determined prior to database lock.

9.6.1 Primary Variable

The primary variable, change from baseline to Week 24 in the 3-day average of total awake time in hours per day spent in the OFF state, will be summarized and analyzed in the mITT and repeated in the PPS.

Descriptive statistics (n, mean, standard deviation, median, minimum, and maximum) will be used to summarize results for OFF time by treatment group and week. Only valid diaries (see **Section 5.3**) post baseline are included in the analyses.

At Week 24, a plot of the cumulative distribution (cumulative of subjects) of average change from baseline in OFF state in hours will be displayed.

The null and alternative hypotheses are as follows:

 H_0 : $\mu_a - \mu_p = 0$

 H_1 : $\mu_a - \mu_p \neq 0$

where μ_a and μ_p are the mean changes from baseline to Week 24 in the 3-day average of total awake time in hours per day spent in the OFF state for the tozadenant and placebo groups, respectively.

The primary analysis will be performed on the change from baseline OFF hours using a mixed model repeated measures ANCOVA that includes fixed terms for country/region, treatment group, week (categorical: 2, 6 12, 18 and 24), interaction between treatment group and week, baseline number of hours of OFF time (covariate) and random effect for subject. This model will allow for estimation of treatment effects (each dose regimen of tozadenant vs placebo) separately at each week as well as averaged across weeks.

Restricted Maximum Likelihood (ReML) estimation will be used with an unstructured covariance structure to model the within-patient error and the Kenward-Roger approximation to estimate the

degrees of freedom. If the model does not converge using the unstructured covariance structure, the AR(1) structure may be considered.

MMRM model assumptions including constant variance, normality of errors and normality of random intercepts will be assessed by residual plots.

CONFIDENTIAL

A test of the null hypothesis of the equality of the adjusted group means in the tozadenant and placebo groups will be performed for each dose regimen of tozadenant using a significance level of 5% (two tailed). Treatment differences will be summarized by least squares means (standard errors) and corresponding 95% confidence intervals.

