11.4.1 Analysis of the Primary Efficacy Variable

The primary efficacy variable will be the change from Baseline to Week 24 in the number of hours per day spent in the OFF state, as assessed by patient-completed PD diaries and averaged over 3 consecutive days. Descriptive statistics will be used to summarize results for the observed OFF time and the change from Baseline in OFF time by treatment group and visit. The primary analysis of the primary variable will be performed on the mITT and based on a mixed model repeated measures (MMRM) analysis of covariance (ANCOVA) that includes terms for treatment group, country, the baseline number of hours of OFF time, and the interaction between treatment group and week. The model will define patient as a random effect and utilize an unstructured covariance pattern. The "country" term in the model may be redefined in the SAP to geographical region (countries grouped together) if some countries do not contribute an adequate number of patients.

Different sensitivity analyses to evaluate the effect of missing observations on the primary analysis findings will be done. The first sensitivity analysis will be performed in the same way as the primary analysis, however for the PPS. A further analysis will utilize the Last Observation Carried Forward (LOCF) approach; missing values will be replaced by the last observed post-baseline value of the variable and the analysis will be performed on the resulting dataset. Finally a multiple imputation method (**Rubin**, 1987; **Little and Rubin**, 1987) will be applied. In addition, for each imputation method, a univariate ANCOVA will be performed at Week 24 which includes the model terms: country/region, treatment group and baseline value.

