3.2 Sample Size Considerations

The primary efficacy endpoint is the change from Baseline to Week 24 in the number of hours per day spent in the OFF state. A sample size of 150 in each group will provide 85% power to detect a difference in mean response of 0.9 hours between tozadenant and placebo assuming the common SD is 2.6 hours and using a two group t-test with a 0.050 two-sided significance level. Across the 3 treatment groups, the total number of patients to be randomized is 450.

Although the sample size calculation is based on the primary endpoint, OFF time, for this study the total sample size of 450 patients is anticipated to yield power to detect treatment differences

in the two key secondary endpoints as summarized in the table below. The assumed treatment differences and standard deviations are based on the findings of the SYN115-CL02 study.

CONFIDENTIAL

Estimated Power for Key Secondary Efficacy Endpoints

Secondary Endpoint	SYN11	Power	
120 mg BID vs. placebo	Treatment	Standard	
	Difference	Deviation	
Good ON time: Number of hours spent in the	1.19	2.64	97%
ON state without troublesome dyskinesia			
UPDRS Parts II + III total score	3.00	8.38	87%

Approximately 645 patients will be screened, assuming a 30% screen failure rate, to randomize 450 patients.

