4.5 Predetermined Covariates and Prognostic Factors

The primary, secondary and exploratory analyses will be based on a mixed model repeated measures (MMRM) ANCOVA, where the covariate in the analysis is the baseline value of the respective response variable. For example, if the number of hours per day spent in the OFF state is being analyzed, the covariate will be the baseline number of hours per day spent in the OFF state. More details are provided in **Sections 9.6.1** to **9.6.3** of this SAP.

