9.6.3 Key Secondary Variables

All secondary variables will be analyzed by the same model as described for the primary outcome variable, with the baseline covariate value being the baseline outcome variable of interest included in the statistical model instead of the baseline number of hours of OFF time in the mITT and PPS. The sensitivity analyses described in **Section 9.6.2** will also be performed for the key secondary outcomes.

The following key secondary efficacy endpoints will be summarized and analyzed:

- Change from baseline to Week 24 in the number of hours per day spent in good ON time, defined as the sum of ON time without dyskinesia and ON time with non-troublesome dyskinesia.
- Change from baseline to Week 24 in UPDRS Parts II (ADL subscale) + III (motor subscale) total scores.

For the UPDRS Part I, II, III, sum of Parts II+III and I – III and Part IV (Part A, B and C and total) if a question making up the total score is missing, the total score for that Part will not be determined for the subject for the given visit, as well as the sum of Parts I - III. Subjects with missing total score will be footnoted.

CONFIDENTIAL

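### The primary MMRM fits one baseline slope to all five weeks; a baseline-by-week term costs almost nothing and can make the Week 24 comparison slightly more precise and more robust

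*SAP*

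**What the plan says.** SAP 9.6.1 treats week as a factor with five levels, "week (categorical: 2, 6 12, 18 and 24", and uses an "unstructured covariance structure to model the within-patient error". Baseline OFF time enters once: "interaction between treatment group and week, baseline number of hours of OFF time (covariate) and random effect for subject". No term lets its slope differ by week.

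The other descriptions agree on baseline. Protocol 11.4.1 lists "terms for treatment group, country, the baseline number of hours of OFF time, and the interaction between treatment group and week", and the synopsis repeats this. SAP 4.5 says only that "the covariate in the analysis is the baseline value of the respective response variable".

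SAP 9.6.3 extends the model: "All secondary variables will be analyzed by the same model as described for the primary outcome variable", with each outcome's own baseline. All six steps of the fixed sequence in SAP 9.6.6 therefore use it, each at Week 24.

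One planned analysis does have its own Week 24 slope. SAP 9.6.2 adds a univariate Week 24 ANCOVA for each imputation method, as a sensitivity analysis.

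**The concern.** The model allows treatment effects, variances and correlations to differ by week, yet holds the baseline effect constant. The documents give no reason for that restriction. If the true slope changes over follow-up, the common slope is a compromise across weeks. The part of Week 24 variation that baseline could explain, beyond what the compromise captures, then stays in the residual.

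Two things follow in that case. The Week 24 standard error is larger than the collected data require. And if the patients still observed at Week 24 differ between arms in baseline OFF time, adjusting with the wrong slope leaves part of that imbalance in the treatment difference.

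**Working it through.** **1. The plan's own power.** SAP 3.2 states: "A sample size of 150 in each group will provide 85% power to detect a difference in mean response of 0.9 hours", with "common SD is 2.6 hours and using a two group t-test with a 0.050 two-sided significance level".

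- SE = 2.6 × √(2/150) = 0.300 h.
- 0.9/0.300 − 1.96 = 1.04, which gives 85.0% power (84.8% with the noncentral t on 298 df).

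The 85% reproduces. It comes from an unadjusted t-test, so the baseline slope plays no part in it.

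**2. Large-sample effect of the restriction.** Let b24 be the true Week 24 slope and b_c the common slope.

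- Week 24 residual variance with a common slope = σ² + (b24 − b_c)² × Var(baseline).
- With slopes by week it is σ².
- SE ratio (by week / common) = √[σ² / (σ² + (b24 − b_c)² Var(baseline))].

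The documents give no baseline SD and no correlation of baseline with each visit. The patterns below are assumptions, scaled so that the Week 24 change SD is the SAP's 2.6 h. With equal SDs at baseline and follow-up, the slope of change on baseline is r − 1. The baseline SD is 2.6 h, except 2.37 h in the last row. Power is for 0.9 h at 150 per arm with no missing data.

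| Correlation, Week 2 to 24 | Slope, Week 2 to 24 | b_c | Residual SD, common / by week | SE ratio | Power, common / by week |
|---|---|---|---|---|---|
| .50 constant | -0.50 | -0.500 | 2.252 / 2.252 | 1.000 | 93.34% / 93.34% |
| .60 to .50 | -0.40 to -0.50 | -0.446 | 2.256 / 2.252 | 0.998 | 93.25% / 93.34% |
| .70 to .50 | -0.30 to -0.50 | -0.369 | 2.277 / 2.252 | 0.989 | 92.82% / 93.34% |
| .80 to .50 | -0.20 to -0.50 | -0.274 | 2.327 / 2.252 | 0.968 | 91.76% / 93.34% |
| .80 to .40 (extreme) | -0.20 to -0.60 | -0.255 | 2.321 / 2.172 | 0.936 | 91.89% / 94.83% |

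Third row in full: the gap is 0.500 − 0.369 = 0.131. Variance = 2.252² + 0.131² × 2.6² = 5.07 + 0.116 = 5.19, so SD = 2.277 and ratio = 2.252/2.277 = 0.989.

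**3. Simulation of both models.** With 450 patients, five weeks, unstructured covariance, 20% random monotone dropout, no country term and 150 runs each, the Week 24 SEs (common, then by week) were:

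- constant slope: 0.2796, 0.2798 (ratio 1.0008; the by-week SE was smaller in 21% of runs);
- first drift row: ratio 0.998;
- second drift row: 0.2865, 0.2831 (ratio 0.988);
- third drift row: 0.2923, 0.2824 (ratio 0.966).

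Mean estimates from the two models differed by at most 0.007 h. Further simulations with about 19% missing gave ratios of 0.989 to 0.990 for drift from -0.20 to -0.45, and 0.965 to 0.969 for drift from -0.15 to -0.60.

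**4. Dropout that depends on baseline and arm.** Protocol 4.3.1 allows discontinuation for worsening symptoms or intolerable adverse events, and Protocol 3.1.2 anticipates 80% completing Part A. As an assumed scenario, dropout rose with baseline OFF time in the active arms only (about 24% missing, against 15% on placebo). The true difference was -0.90 h, with 300 runs:

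| Slope, Week 2 to 24 | Common-slope mean | By-week mean |
|---|---|---|
| constant | -0.90 | -0.90 |
| -0.20 to -0.45 | -0.78 | -0.87 |
| -0.15 to -0.60 | -0.73 | -0.88 |

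Taking an SE of about 0.29 h per trial, the Monte Carlo error of each mean is about 0.29/√300 = 0.017. The by-week means are therefore within two errors of -0.90. The two models differ by 0.09 and 0.15 h; a second simulation of the same kind gave 0.07 to 0.12 h. Against the 0.9 h design effect, 0.07/0.9 = 8% and 0.15/0.9 = 17%.

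To first order the bias is (b24 − b_c) times the between-arm difference in mean baseline among patients still observed. With gaps of 0.131 and 0.226 (third and fourth rows in step 2), a 0.1 h bias needs a baseline difference of about 0.1/0.131 = 0.76 h or 0.1/0.226 = 0.44 h. That is substantial selection, so this is a stress case. The sign depends on which arm loses its high-baseline patients.

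**The case against.** The strongest reply is that both specifications are acceptable. The common-slope model is valid under randomization, and under random dropout the two models give the same answer. The gain is conditional: with a constant slope there is none, and with mild to moderate drift it is about 0.2% to 1.2% of the SE. The Week 24 ANCOVA already fits its own slope and would show a discrepancy. All of this stands as fact, but it does not remove the point. The ANCOVA is a sensitivity analysis on imputed data and cannot replace the primary result, and the term costs almost nothing when it is not needed.

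Three stronger readings are tempting and are not supported:

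- **Week 24 is under-adjusted.** A reader might infer this from the form of the model. It holds only if the Week 24 slope differs from the common slope, and the documents contain no slope, correlation or baseline SD that shows a difference.
- **Power falls below 85%.** With residual SD 2.4 h, baseline SD 2.4 h and slopes from -0.15 to -0.60, simulated power is 83.2% with a common slope and 86.7% by week. But that setting implies a change SD of √(2.4² + (0.60 × 2.4)²) = 2.80 h, above the SAP's 2.6 h. With 2.6 h kept and no missing data, the common-slope model stays above 91% in every row of the table.
- **The key secondary endpoints lose precision.** They share the model, so the same reasoning applies, but nothing was computed for good ON time or UPDRS II + III.

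**Conclusion.** The restriction is real and is stated consistently in the SAP and protocol. It is a missed refinement, not an error: the planned analysis remains valid under randomization with random dropout, and the 85% power is unaffected.

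For OFF time, the Week 24 SE falls by nothing if the slope is constant, about 1% with moderate drift and about 3% to 4% with strong drift. If the slope drifts and dropout depends on baseline differently by arm, the term can also remove a bias of roughly 0.1 h. These sizes rest on assumed slopes, SDs and dropout patterns, and on a linear baseline relation. The priority is low; the case for the change is that it is nearly free.

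**What to change.** Add a baseline-by-week interaction to the model in SAP 9.6.1. Make the same change in Protocol 11.4.1 and the synopsis, and state in SAP 4.5, 9.6.2 and 9.6.3 that it applies to the key secondary and sensitivity MMRMs, using each outcome's own baseline.

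Statistical cost: five slopes in place of one, so 4 extra parameters with 450 patients. If the slope is constant, the Week 24 SE rises by at most about 0.1% to 0.3%. No new data are needed.

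Procedural cost: a protocol text change as well as a SAP revision. SAP Section 1 says the SAP supports a Special Protocol Assessment, whose document was not available here, so the sponsor should check the change against it. SAP Section 8 declares the primary and secondary analyses final, so the term must be prespecified before unblinding. The SAP was written to Amendment No. 1 and the protocol is now at Amendment No. 3, so the change can go into the update that is due in any case.

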7.2 Data Screening

There will be one database freeze during which the data will be exported and the TLFs generated based on this data export. The TFLs will be reviewed by the Sponsor in a blinded data review meeting to identify any final data issues, determine major/minor violations and evaluable subjects analysis set and seek corrections prior to database lock. The Sponsor must approve database lock.

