9.6.2.2 Multiple Imputation Method

The sensitivity analysis described in this section is based on a particular assumption of missing not at random (MNAR), or non-ignorable missingness mechanism. For subjects who withdraw from one of the tozadenant treatment groups, the primary endpoint for missing weeks will be derived using multiple imputation based on the mean in the placebo group. Withdrawals from the placebo group will also be imputed based on the placebo data. Intermittent missing data, that is, data that is missing at one week but present at a later week, will be assumed to be missing at random (MAR) and will be imputed using a method appropriate for that assumption. When the missing data has been imputed, the primary endpoint data will be analyzed as a sensitivity analysis using the same method as the primary analysis.

There are two types of missing data that will be imputed:

- 1. Data that is missing at a specific week but present at a later week (intermittent missing data)
- 2. Data that is missing after a subject drops out (monotonic missing data)

The following process will be used to impute all types of missing values for the primary analysis: Step 1:

 For intermittent missing data, Markov Chain Monte Carlo (MCMC) simulation will be used to impute values.

The MCMC imputation process will follow the general pre-planned guidelines described below. However the ability of the process to converge can be dependent on the amount of data that is missing. Convergence of the process will be assessed after unblinding.

The number of burn in iterations will be set at 200, or higher if deemed necessary. The thinning option will be set to select one out of every 100 iterations to insure sufficient separation from previous iterations. Ten imputations will be the initial setting. Trace plots will be checked for

convergence. Factors included in the MCMC algorithm used to impute the missing values will be randomized treatment and the baseline value of the outcome variable.

CONFIDENTIAL

Step 2:

- 3. For monotone missing data, a regression model will be used to impute values as follows:
- 4. Subjects that do not have a Week 2 value or are in the Placebo arm are selected.
- 5. SAS PROC MI will be used to impute missing values using the Baseline time point.
- 6. The imputed data will be combined with the non-missing tozadenant data to achieve a database with data present for all subjects in the analysis set.

Step 3:

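### SAP 9.6.1 adds a non-identifiable random subject intercept to an unstructured five-visit covariance, and its only fallback is a discretionary, equal-variance AR(1) (low priority)

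*SAP*

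**What the plan says.** The primary model in SAP 9.6.1 has fixed terms for country/region, treatment, week (2, 6, 12, 18, 24) and treatment by week, and then "baseline number of hours of OFF time (covariate) and random effect for subject". It is fitted by REML with an unstructured matrix for the within-patient error and Kenward-Roger degrees of freedom. Protocol 11.4.1 makes the same pairing: "The model will define patient as a random effect and utilize an unstructured covariance pattern".

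The random effect could be read as loose wording for the repeated-measures subject. The model-checking sentence rules that out: "MMRM model assumptions including constant variance, normality of errors and normality of random intercepts will be assessed by residual plots". A literal random intercept is planned.

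For non-convergence there is one sentence: "If the model does not converge using the unstructured covariance structure, the AR(1) structure may be considered". It does not say who decides, when, what happens if AR(1) is not chosen, or whether the random intercept stays in.

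The clause reaches further than the primary endpoint. SAP 9.6.3 states "All secondary variables will be analyzed by the same model as described for the primary outcome variable", with the baseline covariate swapped for the endpoint's own.

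**The concern.** There are two separate problems.

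First, an unstructured matrix already represents every variance and covariance among the five visits. A random intercept adds the same constant to every element of that matrix, and the unstructured part can absorb the constant exactly. The model as written therefore has a parameter with no unique value, and one of its planned diagnostics is aimed at that parameter. Some software may report a singular or failed fit for this reason, and a failed fit is what triggers the fallback.

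Second, AR(1) has one variance for all visits, with or without the random intercept. The treatment effect is read at Week 24 only. A standard error built from a variance pooled over Weeks 2 to 24 is too small if Week 24 is the most variable visit and too large if it is the least. The first Week 24 comparison, 120 mg on OFF time, opens the fixed sequence of six tests in SAP 9.6.6, so the size of that test matters. SAP 9.6.1 lists constant variance among the assumptions to inspect but states no action if it fails. The unstructured model does not need equal variances across visits; the fallback does.

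**Working it through.** **Inputs from the documents.** Five post-baseline visits (SAP 9.6.1); 150 per group, difference 0.9 h, two-sided 0.05, "assuming the common SD is 2.6 hours" (SAP 3.2); 1:1:1 allocation (SAP 3.3); 80% expected to complete Part A (protocol 3.1.2), used below as 20% dropout. **Assumed:** SDs at visits before Week 24 and within-patient correlations. The documents give neither.

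**1. The plan's own figure.** 0.9 / (2.6 × √(2/150)) = 0.9 / 0.3002 = 2.998; power = Φ(2.998 − 1.96) = 85.0% (84.8% by noncentral t). The stated 85% reproduces, and nothing below changes the sample size.

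**2. Parameter count.** An unstructured 5 × 5 matrix has 5 × 6 / 2 = 15 elements. Adding the intercept variance gives 16 parameters; the rank is 15.

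**3. How undetermined the intercept is.** Write the total covariance as R + τJ, where J is all ones. Any τ that leaves R a valid covariance gives the same likelihood. With SD 2.6 h and exchangeable correlation ρ, the upper limit is 2.6² × (1 + 4ρ) / 5, which is 3.5, 4.6 and 5.7 h² for ρ = 0.4, 0.6 and 0.8. In a simulated data set, −2 REML was 2809.814 for τ = 0, 0.3, 0.6 and 0.9 h² alike.

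**4. Does it break the fit?** Setting: 3 × 150 patients, 20% monotone dropout, baseline and four-region terms, three covariance shapes. The unstructured model converged in 900 of 900 trials. With the redundant intercept, a solver that tolerates singularity converged in 240 of 240. Different starting values gave intercept variances 0.24 h² apart on average, while the Week 24 z statistic moved by less than 0.00001. Other software may behave differently.

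**5. Week 24 error if the fallback is used.** As a complete-data approximation for any one-variance model, error = 2 × [1 − Φ(1.96 × pooled SD / Week 24 SD)], with pooled SD the root mean square over visits. For 2.0 to 2.6 h in equal steps, the mean square is (4.0000 + 4.6225 + 5.2900 + 6.0025 + 6.7600) / 5 = 5.335, so the pooled SD is 2.310. The ratio is 2.310 / 2.6 = 0.888 and the error 8.2%. Reversed, the ratio is 2.310 / 2.0 = 1.155 and the error 2.4%.

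The last column fits the fallback as literally written (AR(1) plus random intercept, three parameters, identifiable) in large samples. It covers several correlation shapes, with and without 20% dropout.

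| SD, Week 2 to Week 24 | Approximation | AR(1) + intercept |
|---|---|---|
| 2.6 h throughout | 5.0% | 5.0% |
| 2.3 to 2.6 h | 6.5% | 6.4-6.7% |
| 2.0 to 2.6 h | 8.2% | 8.1-8.8% |
| 2.9 to 2.6 h | 3.8% | about 3.7% |
| 2.6 to 2.0 h | 2.4% | 2.1-2.4% |

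Simulation of the 2.0 to 2.6 h path with 20% dropout gave 9.1% (2,000 trials, SE 0.6; exchangeable correlation 0.6) and, under a different correlation shape, 6.8% (600 trials, SE about 1). Both exceed 5%. The second is less than two standard errors above it, so the upper end of the range is not firmly confirmed.

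**6. Structures with visit-specific variances.** On the 2.0 to 2.6 h and 2.6 to 2.0 h paths, large-sample error was 4.6-5.0% for heterogeneous Toeplitz (9 parameters) and 4.4-5.0% for heterogeneous AR(1) (6 parameters). The Week 24 standard error was at most 0.01% and 2.1% larger, respectively, than with the unstructured matrix.

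**The case against.** The strongest reply is that nothing happens. The estimate does not change when the fit converges, and no fallback was seen in 900 simulated trials. The usual upper bound is then 3 / 900 = 0.33%. Multiplied by an excess of 8.8 − 5.0 = 3.8 points, it adds about 0.013 points to a 5% test. That bound holds only for the settings and solver simulated, but it is a fair reason for low priority, and I accept it as such.

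The plan also has safeguards. SAP 8 and protocol 11.6 call the primary and secondary analyses final and place a blinded review before lock; SAP 7.2 says "The TFLs will be reviewed by the Sponsor in a blinded data review meeting to identify any final data issues". Neither fixes the covariance structure, and an analysis cannot be final while its fallback is optional. The univariate Week 24 ANCOVA in SAP 9.6.2 does not pool variance across visits and could expose the problem, but it is a sensitivity analysis on imputed data and does not stand in for the primary model.

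Four stronger readings are tempting, and the documents do not support them:
- That MMRM convergence will be judged with the treatment codes open. The sentence "Convergence of the process will be assessed after unblinding" in SAP 9.6.2.2 concerns the MCMC imputation. For the MMRM the SAP gives no timing.
- That the redundant term makes non-convergence likely. This was not shown.
- That the trial runs at 8-9% type I error. That figure is conditional on the fallback and on an assumed rising SD; a falling SD makes the test conservative.
- That protocol 11.4.1 is defective for naming no fallback. Protocol 11.0 leaves further detail to the SAP.

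**Conclusion.** The concern holds as a specification fault of low priority. The redundancy is algebra and needs no assumption: the stated primary model is not identifiable in its intercept variance, and the random-intercept check has no target. It leaves the Week 24 result unaffected when the unstructured fit succeeds.

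The fallback is the weaker part of the plan. It is discretionary, applies separately to each endpoint, and assumes equal variances that the main model does not. The conditional error rates rest on assumed SD paths, because the documents give a single SD for OFF time, and they vary modestly with correlation and dropout. Neither the direction of the error nor the probability of reaching the fallback can be determined from the documents, so no overall error rate is claimed.

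**What to change.** In SAP 9.6.1:
- Delete the random subject effect and the random-intercept check.
- Keep REML, the unstructured within-patient covariance and Kenward-Roger.
- Replace the AR(1) sentence with a binding order, applied separately to each endpoint and using the first structure that converges: heterogeneous Toeplitz, then heterogeneous AR(1), both without a random intercept.
- As a last step, name one simple structure with empirical (sandwich) standard errors, and state the degrees-of-freedom method used with it.

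Other orders would be reasonable; what matters is that the order is binding, allows visit-specific variances before the last step, and has an end. Once it is binding, the timing of the convergence check loses its importance. Align protocol 11.4.1 at the next amendment.

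The cost is a small text change to a SAP written to support a Special Protocol Assessment, plus one sentence in the protocol under the approval route in protocol 12.4. The planned estimate does not change if the unstructured model converges. Only in fallback are there more covariance parameters: 9 or 6 instead of 3.
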